5.3 Adjustment for Covariates

Efficacy analyses will be adjusted for baseline values and randomization stratum using ANCOVA, MMRM, or Cochran-Mantel-Haenszel tests, where applicable.

5.4 Handling of Dropouts, Missing Data, and Data Discrepancies

5.4.1 Missing Tissue Eosinophil Count at Week 24

Eosinophil counts will be set to missing if they are collected after subjects have experienced ICE. Subject with missing Week 24 tissue eosinophil count for any reason will be imputed with the eosinophil count collected from the postbaseline unscheduled visit prior to missing. If no eosinophil count is collected postbaseline, the subject will be considered treatment failure for tissue eosinophil response.

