4.5.5 Strategy for Handling Intercurrent Events

If a prohibited/restricted medication is started during the course of the study, the patient may be withdrawn from study treatment and followed for the 12-week follow-up period. In addition, the follow-up EGD may not be performed. Thus, for the analysis of the study product estimand, tissue eosinophil values and TSS scores will be counted as non-responders for binary variables and set to missing for continuous outcomes from the point when an ICE occurs. An appropriate method for handling missing data through statistical modeling (e.g., multiple imputation [MI]) will be used (as detailed in the SAP). The estimand will provide an answer to the question that is crucial to individual subjects:

If I take this study medication as part of my treatment regimen, without adding any further medications that may impact the underlying disease or exit the study prematurely, what improvements in histology and PRO symptoms might be anticipated after 24 weeks?

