11.2.4 Esophago-Gastro-Duodenoscopy with Biopsy

An EGD with biopsy will be performed during the screening period and on Day 169 (± 3 days) or 28 (± 3) days after the last dose of study drug if ET. If the last infusion on Day 141 occurs outside the protocol-specified window, the EGD date should be moved so that it occurs 28 (± 3) days from the date of the last dose, even if this does not fall on Day 169 (± 3 days). Biopsy samples will be collected according to standardized instructions and will be sent to the central laboratory (or designee) for fixing and staining. A blinded central reader will report, among other things, maximum number of eosinophils per hpf and maximum number of tryptase-positive mast cells per hpf, and gastric biopsies will be graded using the Sydney System on inflammation, metaplasia, atrophy, and reactive gastropathy. The Marsh Scale Classification will be used to grade duodenal samples.

Post-treatment EGD results will not be provided to the Investigator and Sponsor until after database lock. The Safety Monitor will review the EGD results and report any issues for escalation to the Medical Monitor and the clinical site, as appropriate, while maintaining the blind.

The screening EGD will be used to determine the following inclusion/exclusion criteria, and the results must be available from the central reader before the patient's eligibility can be verified.

- Inclusion Criterion #3: Baseline endoscopic biopsy with ≥ 30 eosinophils/hpf in 5 hpf in the stomach and/or ≥ 30 eosinophils/hpf in 3 hpf in the duodenum.
- Exclusion Criterion #5: Active *Helicobacter pylori* infection, unless treated and confirmed to be negative prior to randomization and histology per repeat EGD and symptoms still qualify for enrollment after treatment.

Note: A diagnosis of active *H. pylori* at screening may be treated with standard therapies and a repeat EGD completed prior to enrollment to verify that histology criteria are still met and symptoms remain consistent. If *H. pylori* is still present on repeat EGD but UBT and other clinical assessments of active infection are negative, the patient may be randomized into the study.

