15.6 Efficacy Analysis

15.6.1 Primary Efficacy Endpoint Analysis

The first co-primary endpoint will be analyzed using Fisher's exact test. Patients who experience an ICE (i.e., exit the study prematurely or initiate prohibited or restricted medication) prior to the end of Week 24 will be treated as non-responders. Proportion of responders and the associated 95% CI will be presented for each treatment group. The between group difference and the associated 95% CI will also be computed and presented. Sensitivity analysis may be carried out using the Cochran-Mantel-Haenszel (CMH) test stratified by the randomization stratification

factors (Baseline TSS [<28 vs ≥ 28] and disease strata [EG \pm EoD vs EoD]) to assess robustness of Fisher's exact test results.

The rationale for specifying Fisher's exact test as the primary analysis as opposed to specifying CMH is because when a stratum has 100% response for 1 treatment group and 0% response for another treatment group, the CMH test may lose efficiency or not be computable. This is evident from the Phase 2 study outcome.

The second co-primary endpoint will be analyzed by ANCOVA using the imputed data set outlined in the SAP. The LSM, SE, and 95% CI for each treatment group and for the between group difference will be derived from ANCOVA with treatment as a factor, and Baseline PRO TSS (continuous) and EoD without EG (categorical) as covariates. The hypothesis test for the treatment effect will be carried out by the F-test. The synthesizing method will be used to combine the results from multiple imputations.

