Study Day	Study Day 1 is defined as the date on which a subject took the first dose of study drug. Other study days are defined relative to Study Day 1. For visits prior to the first dose of study drug, Study Day is calculated as Visit Date – Day 1 Date. For visits after the first dose, Study Day is calculated as Visit Date – Day 1 Date +1.
Study Drug	AK002 or placebo administered by IV infusion.
Study Week	Study Week for PRO analysis is defined as 7 days a week starting from the day of first dose (Day 1).
Tissue Eosinophil Responder in Disease Status (2 levels; EG ± EoD, EoD)	For EG with/without EoD subjects: Mean eosinophil count \leq 4 cells/hpf in 5 highest gastric hpf and/or mean eosinophil count \leq 15 cells/hpf in 3 highest duodenal hpf. For EoD subjects: Mean eosinophil count \leq 15 cells/hpf in 3 highest duodenal hpf.
Treatment-emergent	Adverse events reported in the clinical database with a date of onset on or after the start date of the first dose of the study drug.
Treatment Responder	Subject with >30% improvement in TSS from baseline and mean eosinophil count \leq 4 cells/hpf in 5 highest gastric hpf and/or mean eosinophil count \leq 15 cells/hpf in 3 highest duodenal hpf.

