4.2.5 Strategy for Handling Intercurrent Events

For the analysis of the study product estimand, tissue eosinophil values and TSS will be counted as non-responders for binary variables and set to missing for continuous outcomes from the point when an ICE occurs. An appropriate method for handling missing data through statistical modeling (e.g., multiple imputation [MI]) will be used (Sections [5.4.1](#), [5.4.2](#), and [6.11](#)). The estimand will provide an answer to the question that is crucial to individual subjects:

“If I take this study drug as part of my treatment regimen, without adding any further medications that may impact the underlying disease or exit the study prematurely, what improvements in histology and PRO symptoms might be anticipated after 24 weeks?”

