6.11.1 Analysis of the First Co-Primary Endpoint

The first co-primary endpoint will be analyzed using the imputed data set (Section 5.4.1). Fisher's exact test (primary analysis) will be conducted comparing AK002 with placebo for the proportion of tissue eosinophil responders. Proportion of responders and the associated 95% confidence interval will be presented for each treatment group. The between group difference and the associated 95% confidence interval will also be computed and presented. A sample SAS code is as follows.

```
* COMPUTE 95% EXACT CONFIDENCE INTERVAL FOR %RESPONSE FOR INDIVIDUAL
TREATMENT ;
ods output BinomialCLs=CL ;
proc freq data=ADEF ;
  table RESP / out=CNTS bin(cl=midp) ;
  by TRTAN ;
run;

* COMPUTE 95% EXACT CONFIDENCE INTERVAL AND FISHERS EXACT P-VALUE FOR
BETWEEN TREATMENT DIFFERENCE ;
ods output FishersExact=PVAL(where=(name1='XP2_FISH'))
RiskDiffCol2=DIFF(where=(row='Difference')) ;
proc freq data=ADEF ;
  table TRTPN*RESP / riskdiff(cl=exact) exact ;
run ;
```

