9.2 Appendix 2: Intercurrent Events

A. Use of any of the following prohibited medications during the course of the study as described

- 1) Immunosuppressive or immunomodulatory drugs (e.g., IL-5 modulators, i.e., benralizumab, reslizumab, mepolizumab; IL-4 and IL-13 antagonists, i.e., dupilumab; calcineurin inhibitors, i.e., cyclosporin, tacrolimus; mTOR inhibitors, i.e., sirolimus, everolimus; anti-metabolites, i.e., azathioprine, methotrexate, 6-mercaptopurine, leflunomide, mycophenolate mofetil; alkylating agents, i.e., cyclophosphamide; TNF inhibitors, i.e., infliximab, adalimumab; anti-IgE antibodies, i.e., omalizumab; and eosinophil-depleting drugs, i.e., pramipexole.
 - a) Use at any point during the study.
- 2) Glucocorticoids
 - a) Initiation of any course of treatment or single use of systemic or swallowed corticosteroids at a dose of >10 mg/day prednisone or equivalent starting at Week 21 and through the end of Week 24. This does not include use of corticosteroids given as pre-infusion prophylaxis or treatment of IRR.

B. Use of restricted medications outside the protocol-defined specifications

- 1) Glucocorticoids
 - a) Discontinuation of a previously stable dose of systemic or swallowed corticosteroids (≤ 10 mg/day prednisone or equivalent) after the screening period.
 - b) Initiation of a new course of systemic or swallowed corticosteroids (≤ 10 mg/day prednisone or equivalent) following the screening period and continuing to at least study Week 21 (within 2 weeks of efficacy assessment at Weeks 23 and 24).
- 2) Proton Pump Inhibitors
 - a) Discontinuation of a previously stable dose of an oral PPI after the screening period and before the end of Week 24.
 - b) Initiation or increase in the dose of an oral PPI following the screening period and continuing to at least study Week 21 (within 2 weeks of efficacy assessment at Weeks 23 and 24).
- 3) Sodium cromolyn
 - a) Discontinuation of a previously stable dose of sodium cromolyn after the screening period and before the end of Week 24

- b) Initiation or increase in the dose of sodium cromolyn following the screening period and continuing to at least study Week 22 (within 1 week of efficacy assessment at Weeks 23 and 24).

C. Discontinuation of Investigational Medical Product

- 1) Discontinuation of study agent due to:
 - a) Infusion-related reaction
 - b) Subject withdrawal
 - c) Meeting study withdrawal criteria (Protocol Section 13.10)

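### SAP 5.4.1, which builds the data for the primary tissue-response test, omits the rule that a patient with an intercurrent event is a non-responder

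*SAP*

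**What the plan says.** **The estimand.** SAP 4.2.5 says that after an ICE "tissue eosinophil values and TSS will be counted as non-responders for binary variables". Protocol 4.5.5 has the same rule: "tissue eosinophil values and TSS scores will be counted as non-responders for binary variables". Protocol 15.6.1 applies it to the first co-primary endpoint: patients with an ICE "prior to the end of Week 24 will be treated as non-responders". None of the three makes an exception for an earlier biopsy.

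**The data rule.** SAP 5.4.1 has three steps. It blanks eosinophil counts taken after an ICE. It then substitutes: "Subject with missing Week 24 tissue eosinophil count for any reason will be imputed with the eosinophil count collected from the postbaseline unscheduled visit". Last, it declares treatment failure, but only for a subject from whom no post-baseline count was collected.

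**The link between them.** SAP 6.11.1 states: "The first co-primary endpoint will be analyzed using the imputed data set", citing 5.4.1, and does not restate the ICE rule. SAP 5.1 sets the default that missing values leave the denominator of a percentage unless the plan specifies otherwise. Protocol section 15 and the SAP introduction both give the SAP precedence over the protocol's statistical methods.

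**The concern.** The estimand makes the outcome depend on the ICE. The data rule makes it depend on whether a biopsy was ever taken. The first step of 5.4.1 creates missing counts because of ICEs, and the second step fills counts missing for whatever reason, including that one. So the data set for a co-primary endpoint can contain an outcome that its own estimand excludes, or no outcome at all for a patient whom the estimand calls a non-responder.

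At stake are the reported response rates, their difference and its confidence interval. If the order of the rules stays open, the choice could be made after treatment codes are known.

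**Working it through.** **1. Plan's own figure.** Inputs from SAP 3.5 and 5.8: 80 per group, response 0.6 versus 0.1, two-sided alpha 0.05. Enumerating both binomial distributions gives Fisher power above 0.9999, in agreement with the stated figure of more than 99%.

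**2. The two rules applied to the same patient.**

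| ICE patient | SAP 4.2.5, Protocol 15.6.1 | SAP 5.4.1 read literally |
|---|---|---|
| (a) Below-threshold unscheduled biopsy before the ICE; Week 24 count absent or blanked | Non-responder | Earlier count substituted: responder |
| (b) Only post-baseline biopsy taken after the ICE | Non-responder | Count collected, then blanked; nothing to substitute; failure sentence not triggered; SAP 5.1 could drop the patient |
| (c) No post-baseline biopsy | Non-responder | Failure |

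Only (c) agrees.

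**3. How likely each route is.** Protocol 11.2.4 says: "An EGD with biopsy will be performed during the screening period and on Day 169", or 28 days after the last dose on early termination. No on-treatment biopsy is scheduled, so (a) needs an unscheduled one and may contain nobody. Route (b) needs only an ICE followed by the scheduled or early-termination biopsy. Protocol 14.2 encourages patients who stop treatment to have it, although Protocol 8.1 allows it to be omitted after a prohibited medication.

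**4. Size per patient, route (a).** Design counts are 0.6 × 80 = 48 and 0.1 × 80 = 8; one patient is 1/80 = 1.25 points. Intervals are exact unconditional 95% limits on the unstandardized difference.

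| Responders, AK002 vs placebo | Difference, points (95% CI) | Fisher p |
|---|---|---|
| 48 vs 8 | 50.0 (35.1 to 63.0) | 2.1e-11 |
| 47 vs 8 (one AK002 responder rescored) | 48.75 (33.8 to 61.9) | 5.8e-11 |
| 48 vs 7 (one placebo responder rescored) | 51.25 (36.4 to 64.1) | 4.3e-12 |

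The direction depends on the arm.

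**5. Size per patient, route (b).** Dropping one non-responder changes AK002 from 48/80 = 60.0% to 48/79 = 60.8%, or placebo from 8/80 = 10.0% to 8/79 = 10.1%. The shift is smaller than in (a), but always raises the rate of the arm concerned.

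**6. Tipping count.** With placebo at 8/80, Fisher p is 0.033 at 19/80 and 0.052 at 18/80. So 48 − 18 = 30 of the 48 AK002 responders would have to be rescored to lose significance.

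**7. Range for the estimate.** The documents give no ICE rate. Assume 5%, 10% or 20% in both arms, and response of 0.6 and 0.1 among patients without an ICE. With every ICE patient a non-responder, the expected differences are 0.5 × 0.95 = 0.475, 0.5 × 0.90 = 0.450 and 0.5 × 0.80 = 0.400, and Fisher power stays above 99.9%. If instead every ICE patient were dropped under (b), the difference would stay at 0.50 on 76, 72 or 64 patients per arm: 2.5, 5 or 10 points higher. These are upper bounds on assumed rates, not forecasts.

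**8. Boundary check.** SAP Table 2 says: "Study Week for PRO analysis is defined as 7 days a week starting from the day of first dose". Week 24 is then Day 1 + 23 × 7 = 162 to Day 24 × 7 = 168. The biopsy window is 169 ± 3, or Days 166 to 172. A biopsy on Day 166 or 167 can therefore precede an ICE that still falls by Day 168.

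**The case against.** **A harmonised reading exists.** SAP 4.2.5 states the non-responder rule and then refers missing data to 5.4.1, whose heading concerns missing counts. A programmer who applies 4.2.5 first has already scored the ICE patient and has nothing to impute. This is fair, and it may be what the sponsor intends. But no text sets that order, and neither 5.4.1 nor 6.11.1 repeats the rule.

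**5.4.1 does not ignore ICEs.** Its first sentence blanks every count taken after one. This stands. The gap lies in the substitution and failure sentences.

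**Reach and visibility.** Route (a) may be empty. SAP 6.11 lists every ICE with the most recent tissue count, and Table 14.1.15 summarises ICEs by arm, so affected patients could be found. Both points stand. They lower the stakes but do not say which score is correct.

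**The early in-window biopsy.** A reader might infer that a Day 166–167 biopsy followed by an ICE by Day 168 is a further error, since SAP Appendix 2 counts higher-dose corticosteroid use "starting at Week 21 and through the end of Week 24" as an ICE. The documents do not support that. SAP 4.2.5 acts from the point of the ICE and leaves the case open; the only conflict is with Protocol 15.6.1, which the SAP supersedes; and the Day 168 boundary comes from a week definition written for the PRO. It is a boundary to define, not a bias.

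**Conclusion.** The concern holds as a conflict within the SAP on a co-primary endpoint: 4.2.5 makes every ICE patient a non-responder, while 5.4.1 read literally makes some responders and leaves others unclassified. Route (b) is the more plausible of the two.

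The size is 1.25 points per patient under (a), and at the design rates about 0.8 (AK002) or 0.1 (placebo) points per patient under (b). Both assume 80 per arm at the design rates; the number of affected patients cannot be derived from the documents and may be zero under (a).

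A reader might infer that the primary test or the sample size is in doubt. The figures do not support that: power stays above 99.9% with all ICE patients counted as failures at assumed rates up to 20%, and 30 rescored AK002 responders would be needed to lose significance. What is affected is the match between the reported estimate and its estimand. It should be fixed.

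**What to change.** In SAP 5.4.1, and by reference in 6.11.1:

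- State that a subject is a tissue non-responder, and stays in the denominator whatever earlier count exists, if an ICE occurs before the end of Week 24 (the Protocol 15.6.1 rule) or if the Week 24 count is blanked because it was taken after an ICE.
- Limit the unscheduled-visit substitution to counts missing without an ICE.
- Reword the failure condition as no evaluable post-baseline count.
- Define the end of Week 24 for the tissue endpoint, which settles the Day 166–168 boundary.
- Apply the same rule to the binary tissue endpoints in 6.12.2 and 6.12.3. Both are analysed by analogy with 6.11.1, so it is an inference, not stated text, that they share its data rule.
- Report the number of substituted counts per arm, for example in Table 14.2.1.1.

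If the sponsor does intend 5.4.1 to govern, 4.2.5 should be changed instead and the departure from the protocol justified.

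The cost is a few sentences and one table row before unblinding. No new data are needed, and the sample size and power statement do not change.

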5.4.2 Missing Daily PRO Scores at Weeks 23–24

PRO daily scores will be set to missing if they are collected after subjects have experienced ICE. For the endpoints of change in the weekly average of PRO TSS, when ≥ 4 of 7 daily scores are available, the weekly average score will be calculated using the available daily scores. (See [Appendix 1](#) for justification of allowing weekly average being calculated from ≥ 4 daily scores.) This calculation implies the missing daily scores are the same as the mean of the non-missing daily scores. When ≥ 4 daily scores are missing, the weekly score will be set to missing. For the calculation of the average PRO TSS over Weeks 23-24, if ≥ 1 weekly score is missing, the biweekly average of Weeks 23–24 will be considered missing.

Missing average of Weeks 23–24 TSS will be imputed using the Markov Chain Monte Carlo (MCMC) method. Baseline tissue eosinophil count and PRO TSS, and disease stratum (EG \pm EoD vs. EoD without EG) will be included along with the average biweekly PRO TSS (W01_02, W03_04, W05_06, ..., W21_22, W23_24) in the multivariate distribution construction. The imputation will be carried out for each treatment group separately and will be executed multiple (50) times (MI). The purpose of MI is to account for the imputation variability in the parameter estimates. An example of the SAS code for this imputation follows.

```
proc mi data=TSS seed=1357986420 n impute=50
  out=TSS_IMMPUTED ;
  by TRTMT ;
  class DISEASE_STRAT ;
  mcmc chain=multiple impute=full initial=em nbiter=200 niter=100 ;
  var B_EOS DISEASE_STRAT (3 levels) B_TSS TSS_W01_02 TSS_W03_04
  ... TSS_W21_22 TSS_W23_24 ;
  run ;
```

After the imputation, the least squares mean (LSM) and standard error (SE) are derived from the conventional ANCOVA from each imputed data set.

These LSM and SE are synthesized to derive the imputation variability-adjusted LSM and SE for each treatment group and for the between treatment difference. These synthesized LSM and SE are then used in the hypothesis test for the between treatment difference. An example of the SAS code for the synthesized LSM comparisons between treatment is as follows.

```
ods output ParameterEstimates=LSMDIF ;
proc mianalyze data=DIFF alpha=0.05 ;
  modeleffects LSM ;
  stderr SE ;
run ;
```

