15.1 Sample Size

A total of approximately 160 patients will be enrolled.

First Co-Primary Endpoint: A sample size of 80 patients per treatment group will have >99% power to demonstrate a greater proportion of responders in AK002 patients than in placebo patients, assuming the proportions of responders are 0.6 and 0.1 in AK002 and placebo groups, respectively.

Second Co-Primary Endpoint: A sample size of 80 patients per group will provide 96% power to detect a statistically significant difference between AK002 and placebo in the mean reduction from baseline in TSS score, assuming a mean reduction of 16.1 points on AK002 versus 8.7 points on placebo and a common standard deviation of 12.5 points (AK002-003 data on file). Eighty patients per group will provide 96% power to pick up a difference between placebo and AK002 of 7.4 in TSS with a mean Baseline TSS of 30 and a standard deviation (change from baseline) of 12.5. These assumptions are based on data observed in the Phase 2 AK002-003 study.

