3.1 General Description

This is a Phase 3, multicenter, randomized, double-blind, placebo-controlled study to evaluate the efficacy and safety of AK002 in subjects with moderate-to-severe EG and/or EoD who have an inadequate response, lost response, or were intolerant to standard therapies. Subjects enrolled in the study will receive 6 infusions of placebo or AK002 administered every 4 weeks and will be followed for 12 weeks after the last dose unless subjects elect to enter the optional long-term extension study.

Subjects who have signed the informed consent form (ICF) will be screened within 35 days prior to Study Day 1.

The study will be carried out as follows:

- An 18 to 45-day screening period with baseline evaluations, including active symptoms of disease (gathered by PRO questionnaire) and EGD with biopsy.
- Prior EGD may be used for eligibility as long as it was collected within 30 days of the first screening visit for the AK002-016 study and was performed and centrally evaluated for the AK002-016 study.
- If subjects meet histology and symptom eligibility criteria, they will be randomized after being stratified by the highest weekly TSS of disease activity recorded during the screening period (<28 or \geq 28 strata) and whether the subject has EG with or without EoD (EG \pm EoD) or EoD without EG. The interactive response technology (IRT) will randomly assign subjects 1:1 to receive AK002 or placebo.

- Pre-study medications and dietary restrictions will remain unchanged throughout the study. Systemic or topical steroids above 10 mg prednisone will not be allowed except due to unforeseen medical circumstances where it is deemed to be medically necessary to treat an unrelated medical condition or when given as a premedication prior to infusion or to treat an IRR that occurs during infusion (see Section [6.3](#) and Protocol Section 8.1).
- Eligible subjects will receive the first dose of placebo or AK002 (1 mg/kg) on Day 1, with premedication of 60 mg oral prednisone 12–24 hours prior to the start of the infusion.
- If the study drug is well tolerated (no stopping rules being met), subjects will receive additional doses of placebo or AK002 (3 mg/kg) on Days 29, 57, 85, 113, and 141. With the exception of Day 1, steroid premedication will only be allowed with the written approval of the Medical Monitor.
- Subjects will remain at the site for at least 1 hour of observation following the end of the infusion.

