3.5 Determination of Sample Size

A total of approximately 160 subjects will be enrolled.

First Co-Primary Endpoint: A sample size of 80 subjects per treatment group will have >99% power to demonstrate a greater proportion of tissue responders at Week 24 in AK002 subjects when compared to placebo subjects, assuming the proportions of responders are 0.6 and 0.1 in AK002 and placebo groups, respectively.

Second Co-Primary Endpoint: A sample size of 80 subjects per group will provide 96% power to detect a statistically significant difference of 7.4 points between AK002 and placebo in the mean reduction from baseline in TSS at Weeks 23–24, assuming a common standard deviation of 12.5 points and a population mean baseline TSS of 30 points.

4. Definitions

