5.8 Multiple Comparisons/Multiplicity Adjustment

To control for the family-wise type-I error rate, the following testing procedures will be implemented:

Test each co-primary efficacy endpoint at 2-sided $\alpha=0.05$ level.

- If $p\leq 0.05$ for both co-primary endpoints, then reject the null hypothesis that AK002 is no different from placebo and accept the alternative hypothesis that AK002 is superior to placebo in reducing tissue eosinophil count and TSS score.
- If $p\leq 0.05$ for both co-primary endpoints, the hypothesis tests for the secondary endpoints will proceed in the prespecified order.
- If $p>0.05$ for either co-primary endpoint, the null hypothesis is accepted. No hypothesis test will be performed for the secondary endpoints.
- The issue of multiplicity of secondary endpoints will be handled by statistical testing of these outcomes in a hierarchical fashion. The order of secondary endpoints is described in Section 2.2. If at any point during the analysis of the secondary endpoints, the statistical test is not significant at 2-sided $\alpha=0.05$ level, the hypothesis testing procedure will stop. AK002 will be deemed superior to placebo for all endpoints prior to the stop.

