6.12.5 Change in Weekly TSS Over Time

Prior to the analysis, the missing weekly TSS scores will be imputed similarly to the imputation for the missing biweekly PRO TSS scores (Section 5.4.2). The imputed data sets will be analyzed using the mixed model for repeat measures (CCI [REDACTED]) with treatment, week, and treatment-by-week interaction as fixed factors, baseline PRO TSS (continuous), and EoD without EG (Y/N) as covariates, and subject as repeated measure unit over time. The model will use change from baseline in the weekly TSS from Weeks 1 through Week 24.

The model variance-covariance matrix will be unstructured. If the computation does not converge, the covariance matrix will take the form of Toeplitz, AR(1), and compound symmetry, whichever converges first. The improved Kenward-Rodger's method (SAS KR2 option) will be used to derive the denominator degrees-of-freedom. The LSM and 95% CI for the between group difference will be estimated using the simple contrast at each week.

A sample SAS code is provided as follows.

```
proc mixed data=ADEF method=REML ;
  class TRTPN USUBJID WEEK ;
  model CHG = B_TSS DISEASE_STRAT TRTPN WEEK TRTPN*WEEK / ddfm=KR2 ;
  repeated WEEK / subject=USUBJID(TRTPN) type=UN ;
  lsmeans TRTPN*WEEK / pdiff cl ;
run ;
```

The rationale for using the CCI [REDACTED] model is that this analysis is appropriate assuming subjects with missing data behave similarly to other subjects in the same treatment group. Having included in the model baseline symptom score (TSS), disease status (EG \pm EoD vs. EoD), and response trajectory prior to missing, it is reasonable to believe that the missing data are either completely at random (MCAR) or at random (MAR) in this setting. In another words, if missing mechanism is not MCAR, it is likely explainable by the above model covariates and response trajectory. A sample SAS code is included in [Appendix 4](#).

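### The Weeks 23–24 rule in SAP 5.4.2 discards a valid observed week whenever its partner is missing; the loss of precision is small and cheap to avoid

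*SAP*

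**What the plan says.** SAP 5.4.2 builds the endpoint in two steps. At weekly level, "when ≥ 4 of 7 daily scores are available, the weekly average score will be calculated using the available daily scores"; with four or more diaries absent the weekly score is missing. At two-week level, one missing week is enough: "the biweekly average of Weeks 23–24 will be considered missing".

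The missing average is filled by MCMC multiple imputation, by treatment group. The variables are baseline eosinophil count, baseline TSS, disease stratum and the biweekly averages from Weeks 1–2 to Weeks 23–24. The code in 5.4.2 and Appendix 4 has the same variables, and no weekly score appears in either.

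Both sensitivity analyses in SAP 6.11.5 start from this imputed biweekly data set. A biweekly value is reset to missing if at least four of its daily scores fall on or after the intercurrent event, and is then re-imputed. In the first of these analyses the re-imputation for AK002 patients is placebo-based.

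For the last secondary endpoint, SAP 6.12.5 works by week: "the missing weekly TSS scores will be imputed similarly to the imputation for the missing biweekly PRO TSS scores".

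Appendix 1 of the SAP supports the 4-of-7 diary rule. The documents give no reason for requiring both weeks.

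**The concern.** Half of a co-primary endpoint can be measured under the SAP's own completeness standard and still be ignored. The observed week is the best available predictor of the two-week average, yet the imputation model sees nothing later than Weeks 21–22. The patients affected are those with exactly one of the two weeks valid, whether because diaries were skipped or because an intercurrent event fell early in Week 24. What is at stake is some precision on the second co-primary. For patients with an early Week 24 event, an observed pre-event week is also replaced in the sensitivity analyses.

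**Working it through.** **1. The plan's power figure.** SAP 3.5 states: "A sample size of 80 subjects per group will provide 96% power to detect a statistically significant difference of 7.4 points", "assuming a common standard deviation of 12.5 points and a population mean baseline TSS of 30 points". Allocation is 1:1 and the test is two-sided at 0.05 (SAP 3.1 and 5.8). Protocol 15.1 gives the same difference: 16.1 − 8.7 = 7.4.

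- SE of the difference = 12.5 × √(2/80) = 1.976.
- Power = Φ(7.4/1.976 − 1.960) = Φ(1.784) = 96.3%. The noncentral t with 158 df gives 96.1%.

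The stated 96% reproduces.

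**2. Diary counts.** 4 + 4 = 8 of 14 diaries (57%) counts as observed. 7 + 3 = 10 of 14 (71%) counts as missing and is imputed.

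**3. Events in Week 24.** SAP Table 2 counts study weeks from Day 1, so Week 23 is Days 155–161 and Week 24 is Days 162–168. Take an event on Day d of Week 24, with complete diaries.

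- If the event-day diary is kept, Week 24 has d − 161 scores. It fails when d − 161 < 4, that is on Days 162–164.
- If the event-day diary is dropped, it has d − 162 scores and fails on Days 162–165.
- Under the 6.11.5 reset, days on or after the event number 168 − d + 1. This is at least 4 when d ≤ 165.

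So only events on about the first three or four days of Week 24 cost the patient a valid Week 23.

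**4. Effect on the standard error.** The documents give neither the share affected, q, nor the week-to-week correlation, so everything in this step is assumed: between-patient SD 10; weekly deviations with SD 4–6 and lag-1 correlation 0.3–0.8; q = 5–20%. Baseline covariates are left out. Let V be the variance of the Weeks 23–24 mean given the predictors, and σ² its total variance. The large-sample SE is inflated by √[1 + q/(1−q) × V/σ²].

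| Weekly SD, lag-1 correlation | σ² | V, earlier biweekly averages only | V, Week 23 added | Cut in V |
|---|---|---|---|---|
| 4, 0.8 | 114.4 | 7.27 | 1.48 | 80% |
| 6, 0.3 | 123.4 | 24.4 | 8.5 | 65% |
| 6, 0.5 | 127.0 | 24.99 | 7.01 | 72% |

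- Smallest gain (SD 4, correlation 0.8, q = 5%): inflation 1.0017 under the SAP rule against 1.0003 with the week kept, a fall of 0.1%.
- Largest gain (SD 6, correlation 0.5, q = 20%): √(1 + 0.25 × 24.99/127.0) = 1.0243 against √(1 + 0.25 × 7.01/127.0) = 1.0069, a fall of 1.7%.

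On an SE of 1.976 that is about 0.003 to 0.03 TSS points, against a target difference of 7.4.

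**5. Effect on power.** A second set of assumptions takes q = 2–15% and a correlation of 0.79–0.97 between adjacent weekly scores. Earlier biweekly averages then explain 55–92% of the variance of the endpoint, and adding Week 23 raises this to 90–99%. Effective n per arm = 80 / [1 + q/(1−q) × (1 − R²)].

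| Case | SAP rule | Observed week kept |
|---|---|---|
| q = 15%, R² 0.553 → 0.898 | n 74.2, power 95.0% | n 78.6, power 96.0% |
| q = 5%, R² 0.553 → 0.898 | n 78.2, power 95.9% | n 79.6, power 96.2% |
| q = 2%, R² 0.921 → 0.985 | n 79.9, power 96.3% | n 80.0, power 96.3% |

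If affected patients contributed nothing at all, power would be 95.4% at q = 5% (n = 76) and 94.4% at q = 10% (n = 72).

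**The case against.** The strongest reply is that this does not matter. The gain is hundredths of a TSS point at most, and no conclusion would plausibly turn on it. The large per-patient variance cut says little about the trial. The upper shares of 15–20% have no support in the documents. Several features point to fewer: diary completion is an entry criterion (Protocol 7.3), payment requires at least four diaries a week (17.6), reminders are offered (Appendix 7) and compliance is checked at visits (Section 12). Requiring both weeks also keeps every observed value equal to the endpoint as defined. All of this stands, and it is why the point is minor.

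A reader might also infer more than the documents support:

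- **That any Week 24 event costs the patient Week 23.** With complete diaries, an event on Day 166 or later leaves Week 24 valid and nothing is discarded. The last infusion is planned for Day 141 (±3), so stopping study drug would not normally first occur in Week 24. Appendix 2 does list medication events that can.
- **That the sensitivity analyses put placebo-based values in place of weeks lost to skipped diaries.** The 6.11.5 reset depends on the event date, so ordinary skipped diaries do not trigger it.
- **That 6.12.5 contradicts 5.4.2.** Its endpoint is the weekly course of TSS, so imputing by week follows from that endpoint. It shows that weekly imputation is already planned, and no more.

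None of these replies gives a reason to leave the observed week out of the predictors.

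**Conclusion.** The point holds as a cheap improvement. As written, 5.4.2 and its code leave a valid in-window week out of both the outcome and the imputation model. For events early in Week 24, the separate reset in 6.11.5 also replaces the two-week value in the sensitivity analyses. Keeping the week would lower the trial-level SE by about 0.1–1.7%, with power moving by at most about 1 point. Both ranges rest on the assumed variances, correlations and shares above, and on missing weeks being unrelated to the unseen score given the predictors.

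Two stronger conclusions are not supported. The trial is not underpowered because of this rule: power stays at 95.0% or above across the imputation scenarios. Nor does the rule favour AK002: it is prespecified and identical in both arms, and bias would need missingness, or its link to symptoms, to differ by arm.

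**What to change.** - **SAP 5.4.2 and Appendix 4:** replace TSS_W23_24 with TSS_W23 and TSS_W24 in the imputation variables. Impute, average the two completed values, and then compute the change score from that average.
- **SAP 6.11.5:** make the same replacement in both code blocks. Apply the post-event reset to Week 23 and Week 24 separately, so that a Week 23 completed before the event is kept. Changing 5.4.2 alone would not achieve this.

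The endpoint, the estimand and the alpha are unchanged. The cost is one more variable in the imputation model and a modest rewrite of the imputation and sensitivity code, to be settled before unblinding.
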